#### 12.4 Overall survival censoring rules

Situation	Date Death or Censoring	Outcome
Death at any timepoint	Date of death	Death
Lost to follow-up immediately after 1st dose of study drug	Date of 1st dose study drug	Censored
Not known to have died at or after the analysis cutoff date	The date last known alive before data analysis cutoff	Censored
Known to have died after the analysis cutoff date	Date of data analysis cutoff	Censored

### 12.5.1 Events Of Clinical Interest

The Events of Clinical Interest (ECIs) have been identified based on preclinical findings, emerging data from clinical studies relating to acalabrutinib, and pharmacological effects of approved BTK inhibitor. The AEs selected for dedicated analysis were evaluated using Standardized MedDRA Queries (SMQs), where available, by SOC, or by Sponsor-defined baskets of MedDRA Adverse Event Grouped Terms.

Category name	Sub-category name	Definition
Cardiac events		
 
SOC Cardiac disorders
 

	Atrial fibrillation	
 
PT Atrial fibrillation
 
PT Atrial flutter
 

Cytopenias – Anemia		
 
SMQ Haematopoietic erythropenia [narrow + broad]
 

Cytopenias – Leukopenia		
 
SMQ Haematopoietic leukopenia [narrow + broad]
 

	Neutropenia	
 
PT Febrile Neutropenia
 
PT Neutropenia
 
PT Neutropenic infection
 
PT Neutropenic sepsis
 
PT Neutrophil count decreased
 
PT Neutrophil percentage decreased
 

	Other Leukopenia	
 
SMQ Haematopoietic leukopenia [narrow + broad] excluding PTs for neutropenia above
 

Cytopenias - Thrombocytopenia		
 
SMQ Haematopoietic thrombocytopenia [narrow + broad]
 

Hemorrhage		
 
SMQ Haemorrhage terms (excl laboratory terms)
 

	Major hemorrhage	
 
As per Acerta definition in Appendix 12.5.2 below
 

Hepatic Events		
 
SMQ [narrow] Hepatic failure, fibrosis and cirrhosis and other liver damage-related conditions
 
SMQ [narrow] Liver related investigations signs
 
SMQ [narrow] Hepatitis, non-infectious
 

Hypertension		
 
SMQ Hypertension [narrow]
 

Infections		
 
SOC Infections and infestations
 

Interstitial lung disease/Pneumonitis		
 
SMQ [narrow] Interstitial lung disease
 

Second primary malignancies		
 
SMQ Malignant or unspecified tumours and SMQ Myelodysplastic syndrome [narrow]
 

	Second primary malignancies (excluding skin)	
 
SMQ Malignant or unspecified tumours and SMQ Myelodysplastic syndrome [narrow], excluding skin (i.e. exclude SMQ Skin neoplasms, malignant and unspecified)
 

Tumor lysis syndrome		
 
PT Tumour lysis syndrome
 

MedDRA version 20.1

'No additional criteria' means only SAE, AE leading to study drug discontinuation, and deaths within specified window will be selected for narratives.

'Any' means any subject with a PT in the category will be selected for narratives.

## 12.5.2 Major Hemorrhage

Major hemorrhage is defined as any hemorrhagic event that is serious, or Grade  $\geq 3$  in severity, or that is a central nervous system (CNS) hemorrhage (any severity grade).

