12. Requires or receiving anticoagulation with warfarin or equivalent vitamin K antagonists (e.g., phenprocoumon) within 7 days of first dose of study drug
13. Requires treatment with proton-pump inhibitors (e.g., omeprazole, esomeprazole, lansoprazole, dexlansoprazole, rabeprazole, or pantoprazole). Subjects receiving proton-pump inhibitors who switch to H₂-receptor antagonists or antacids are eligible for enrollment to this study.
14. History of clinically significant stroke within 6 months before the first dose of study drug
15. History of clinically significant intracranial hemorrhage within 6 months before the first dose of study drug. Cases of Grade 1 radiographic-only hemorrhage (e.g., old hemosiderin) may be allowed per the discretion of the study medical monitor.
16. Major surgical procedure within 28 days of first dose of study drug. Note: If a subject had major surgery, they must have recovered adequately from any toxicity and/or complications from the intervention before the first dose of study drug. If a subject had a recent surgery for recurrent or progressive tumor, then the surgery must have confirmed the recurrence. For core or needle biopsy, a minimum of 7 days must have elapsed before enrollment, the craniotomy or intracranial biopsy site must be adequately healed and free of drainage or cellulitis, and the underlying cranioplasty must appear intact at the time of first dose.
17. ANC $<1.5 \times 10^9/L$ or platelet count $<100 \times 10^9/L$ or hemoglobin <8.0 g/dL

18. Total bilirubin >1.5 x upper limit of normal (ULN)
19. AST or ALT >3.0 x ULN
20. Estimated creatinine clearance of <30 mL/min, calculated using the formula of Cockcroft and Gault $[(140 - \text{Age}) \cdot \text{Mass (kg)}] / (72 \cdot \text{creatinine mg/dL})$ • multiply by 0.85 if female]
21. Breastfeeding or pregnant
22. Concurrent participation in another therapeutic clinical trial
23. Known history of HIV, serologic status reflecting active hepatitis B or C infection, or any uncontrolled active systemic infection
 - a. Subjects who are hepatitis B core antibody (anti-HBc) positive and who are surface antigen negative will need to have a negative polymerase chain reaction (PCR) result before enrollment. Those who are AbsAg positive or hepatitis B PCR positive will be excluded.
 - b. Subjects who are hepatitis C antibody positive will need to have a negative PCR result before enrollment. Those who are hepatitis C PCR positive will be excluded.

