### **10.6.1 Adverse Events**

The Medical Dictionary for Regulatory Activities (MedDRA v20.1 or later) will be used to code all AEs to a system organ class and a preferred term. The severity of the AE will be assessed by National Cancer Institute (NCI) Common Terminology Criteria for Adverse Events (CTCAE) Version 4.03. Study drug-related AEs are those assessed by investigator as related.

All AE tables will be summarized by treatment cohort.

TEAEs are defined as those events that occur or worsen on or after the first dose of study drug (acalabrutinib), through the treatment phase, and within 30 days following the last dose of acalabrutinib.

TEAEs will be summarized by system organ class (SOC) and preferred terms (PTs) as well as preferred terms only in descending order of frequency, by CTCAE severity grade.

Drug-related TEAEs, treatment-emergent serious adverse events (TESAEs), TEAEs leading to study drug discontinuation or dose modifications or dose delay will be summarized by PTs in descending order of frequency and by CTCAE severity grade.

Death information is reported in the study exit case report form (CRF) and death information CRF for all deaths. Incidences of deaths are to be reported, along with the primary cause of death.

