### Search Strategy:

- I. Use standardized MedDRA v20.1 Query:
  - o Haemorrhage terms (excl laboratory terms) (SMQ) [20000039]
  
- II. Identify Major Events that are a subset of the Haemorrhage SMQ:
  - o Grade  $\geq 3$  AE
  - o Any SAE
  - o All Grades of CNS hemorrhage

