### CNS hemorrhage Preferred Terms (MedDRA v20.1):

Acute haemorrhagic leukoencephalitis	Haemorrhagic transformation stroke
Basal ganglia haematoma	Intracerebral haematoma evacuation
Basal ganglia haemorrhage	Intracranial haematoma
Basilar artery perforation	Intracranial tumour haemorrhage
Brain contusion	Intraventricular haemorrhage
Brain stem haematoma	Intraventricular haemorrhage neonatal
Brain stem haemorrhage	Meningorrhagia
Brain stem microhaemorrhage	Ocular retrobulbar haemorrhage
Central nervous system haemorrhage	Optic disc haemorrhage
Cerebellar haematoma	Optic nerve sheath haemorrhage
Cerebellar haemorrhage	Periventricular haemorrhage neonatal
Cerebellar microhaemorrhage	Pituitary haemorrhage
Cerebral aneurysm perforation	Putamen haemorrhage
Cerebral aneurysm ruptured syphilitic	Ruptured cerebral aneurysm
Cerebral arteriovenous malformation haemorrhagic	Spinal cord haematoma
Cerebral artery perforation	Spinal cord haemorrhage
Cerebral haematoma	Spinal epidural haematoma
Cerebral haemorrhage	Spinal epidural haemorrhage
Cerebral haemorrhage foetal	Spinal subarachnoid haemorrhage
Cerebral haemorrhage neonatal	Spinal subdural haematoma
Cerebral microhaemorrhage	Spinal subdural haemorrhage
Encephalitis haemorrhagic	Subarachnoid haematoma
Epidural haemorrhage	Subarachnoid haemorrhage
Extradural haematoma	Subarachnoid haemorrhage neonatal
Haemorrhage intracranial	Subdural haematoma
Haemorrhagic cerebral infarction	Subdural haematoma evacuation
Haemorrhagic stroke	Subdural haemorrhage
Subdural haematoma evacuation	Subgaleal haematoma
Subdural haemorrhage	Thalamus haemorrhage
Subdural haemorrhage neonatal	Traumatic intracranial haemorrhage

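### The SAP's any-grade CNS hemorrhage term list includes two bleeds that lie outside the CNS, so a minor scalp or orbital bleed could be counted as major hemorrhage against the SAP's own definition

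*SAP*

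**What the plan says.** SAP 12.5.2 gives the definition: "Major hemorrhage is defined as any hemorrhagic event that is serious, or Grade" 3 or above, "or that is a central nervous system (CNS) hemorrhage (any severity grade". For a bleed that is neither serious nor Grade 3 or higher, the CNS site alone decides whether it is major.

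The search strategy in the same section has two steps. The first is a gate: "Use standardized MedDRA v20.1 Query", naming the Haemorrhage SMQ without laboratory terms. The second keeps, within that SMQ, events of Grade 3 or higher, all SAEs, and CNS hemorrhage of every grade. A list headed as CNS hemorrhage preferred terms in MedDRA v20.1 follows. It contains "Subgaleal haematoma", "Ocular retrobulbar haemorrhage" and "Intracranial tumour haemorrhage", together with general terms such as Haemorrhage intracranial and Central nervous system haemorrhage.

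On coding, SAP 10.6.1 states "MedDRA v20.1 or later) will be used to code all AEs". SAP 12.5.1 lists major hemorrhage as a sub-category of the hemorrhage event of clinical interest and cites MedDRA 20.1. AE tables are presented by cohort (SAP 10.6.1), with 15 subjects on 200 mg BID and 9 on 400 mg QD (SAP 3.2). SAP section 5 says that no hypothesis is tested.

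**The concern.** The definition and the list that implements it do not agree. The any-grade route to major is worded as CNS hemorrhage. A subgaleal haematoma lies in the scalp, outside the skull, and a retrobulbar haemorrhage lies in the orbit behind the eye. A program that follows the list would label a mild, non-serious event of either kind as major. A reader of the definition would not expect it to be counted.

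The list also works only through the coded term. Every study tumor here is a glioblastoma, so a bleed into the tumor is a CNS bleed however it is coded. The only listed term that names a tumor also names its site. The SAP has no step that looks at the reported site of an event whose coded term names none.

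Safety is a primary objective, and hemorrhage is the first warning listed for the drug (protocol 3.9.2). The final analysis is descriptive and covers 24 subjects, so one event placed in the wrong row would be visible.

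**Working it through.** The documents report no major-hemorrhage count or rate, so there is no figure to reproduce. The check compares definition with list, then works out what one reclassified subject would do.

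**1. The list, term by term.** As it reads in the SAP, the list has 60 entries. Two terms appear twice (Subdural haematoma evacuation and Subdural haemorrhage), which leaves 58 distinct terms. The repetition does not affect any count.
- Clearly outside the CNS by name: 2 (subgaleal, retrobulbar).
- Arguable: 2 (Optic disc haemorrhage, Optic nerve sheath haemorrhage).
- Naming a tumor: 1, and it specifies an intracranial site.
- Tumor or postoperative bleed with no site: none. The list is alphabetical, so loss of an entry after the last one shown cannot be fully excluded, although the list looks complete.

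**2. When the two non-CNS terms change the result.** An event counts as major if it is in the SMQ and is serious, Grade 3 or higher, or on the list. For a subgaleal or retrobulbar event in the SMQ:
- serious or Grade 3 or higher: major with or without the list;
- non-serious and Grade 1 or 2: major only because of the list, and not a CNS hemorrhage under the definition.

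The over-count is confined to the second line. It assumes that both terms pass the SMQ gate. The SAP lists them as if they do, but does not show the SMQ's contents.

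**3. When a study-tumor bleed is missed.** All of these must hold together: the event is non-serious; it is Grade 1 or 2; and it is coded to a term that names no site and is not on the list. A bleed coded with its site is caught by "Intracranial tumour haemorrhage" or by one of the general intracranial terms.

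**4. MedDRA version.** Coding may use v20.1 or a later version, while the SMQ and the list are fixed at v20.1. No rule carries them forward. If v20.1 is used for coding, there is no effect. If a later version is used, terms added or renamed since v20.1 are not covered.

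**5. Effect of reclassified subjects.** The rate is x/n. The exact (Clopper-Pearson) 95% limits are: lower = the 0.025 quantile of Beta(x, n−x+1), or 0 when x=0; upper = the 0.975 quantile of Beta(x+1, n−x). For x=0 the upper limit is 1 − 0.025^(1/n); for n=15 this is 1 − 0.782 = 21.8%.

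| Group | n | One subject (1/n) | 0 events (95% CI) | 1 event (95% CI) | 2 events (95% CI) |
|---|---|---|---|---|---|
| 200 mg BID | 15 | 6.7 points | 0% (0 to 21.8) | 6.7% (0.2 to 31.9) | 13.3% (1.7 to 40.5) |
| 400 mg QD | 9 | 11.1 points | 0% (0 to 33.6) | 11.1% (0.3 to 48.2) | 22.2% (2.8 to 60.0) |
| Both | 24 | 4.2 points | 0% (0 to 14.2) | 4.2% (0.1 to 21.1) | 8.3% (1.0 to 27.0) |

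The documents do not give the number of subjects affected. The range of 0 to 2 is an assumption for illustration, and zero is quite possible.

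**The case against.** The strongest reply is that this is a descriptive sub-category that no decision depends on. No hypothesis is tested, and no stopping rule or threshold in the documents uses the major-hemorrhage rate. A shift of 1/15 or 1/9 would follow from misplacing one subject in any AE category of these cohorts. All of this stands and limits the point to a minor correction. It does not remove the mismatch between definition and list.

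Two stronger readings are tempting, and the documents support neither.

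*That the rate is wrong in both directions because real bleeding into the study tumor is left out.* The under-count is only conditional. The list already has a term for bleeding in an intracranial tumor and several general intracranial and CNS terms. Serious or Grade 3 or higher events in the SMQ count whatever their site. The documents do not show that a term without a site exists within the SMQ, or that any event will be coded to one. Such an event, if in the SMQ, would still appear in the parent hemorrhage category, and as a TEAE it would appear by preferred term and grade. It would lose only the label of major.

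*That counting Grade 1 CNS blood as major is itself an error.* The protocol's exclusion criterion 15 says "Cases of Grade 1 radiographic-only hemorrhage (e.g., old hemosiderin) may be allowed per the discretion of the study medical monitor", and protocol 3.7 sets its specific intracranial-hemorrhage action from Grade 2, so a reader might infer a conflict. There is none. Any-grade counting is the sponsor's explicit choice. The entry criterion concerns blood present before dosing. A pre-existing condition that has not worsened is not an AE (protocol 6.1.1), and a TEAE must occur or worsen on or after first dose (SAP 10.6.1). The Grade 2 rule governs withholding drug, not the counting of events.

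It is also fair to say that removing two terms leaves the two optic terms to judgment.

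**Conclusion.** The point holds in a limited form. The any-grade list contains two terms outside the CNS by name, so a non-serious Grade 1 or 2 event under either would be counted as major against the definition. This rests on one assumption that the documents do not settle: that both terms lie within the Haemorrhage SMQ.

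The missing provision for a low-grade, non-serious study-tumor or operative-site bleed coded without a site is a gap in the safeguards, not a demonstrated under-count. The version mismatch is real on the page, but has an effect only if AEs are coded in a version later than v20.1.

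The effect is 6.7 or 11.1 points per reclassified subject, for an unknown number that may be zero. This is a minor correction that does not alter the trial's design or any decision rule.

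**What to change.** In SAP 12.5.2:

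1. Remove "Subgaleal haematoma" and "Ocular retrobulbar haemorrhage" from the any-grade list. Events under these terms still count as major if serious or Grade 3 or higher. Record whether the two optic terms are meant to be CNS.
2. Before database lock, check the reported site of non-serious Grade 1 or 2 events in the Haemorrhage SMQ, and count those in the brain or study tumor as CNS hemorrhage. This check cannot find events that are coded outside the SMQ.
3. Run the SMQ and the list in the MedDRA version used to code the AEs, and state that version.

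The cost is a few lines of text and a look at the low-grade hemorrhage events in 24 subjects. The drawback is a small departure from the sponsor's standard definition, which can be kept as a second row so that comparison with other acalabrutinib studies is preserved.

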### Search Strategy:

- I. Use standardized MedDRA v20.1 Query:
  - o Haemorrhage terms (excl laboratory terms) (SMQ) [20000039]
  
- II. Identify Major Events that are a subset of the Haemorrhage SMQ:
  - o Grade  $\geq 3$  AE
  - o Any SAE
  - o All Grades of CNS hemorrhage

### CNS hemorrhage Preferred Terms (MedDRA v20.1):

Acute haemorrhagic leukoencephalitis	Haemorrhagic transformation stroke
Basal ganglia haematoma	Intracerebral haematoma evacuation
Basal ganglia haemorrhage	Intracranial haematoma
Basilar artery perforation	Intracranial tumour haemorrhage
Brain contusion	Intraventricular haemorrhage
Brain stem haematoma	Intraventricular haemorrhage neonatal
Brain stem haemorrhage	Meningorrhagia
Brain stem microhaemorrhage	Ocular retrobulbar haemorrhage
Central nervous system haemorrhage	Optic disc haemorrhage
Cerebellar haematoma	Optic nerve sheath haemorrhage
Cerebellar haemorrhage	Periventricular haemorrhage neonatal
Cerebellar microhaemorrhage	Pituitary haemorrhage
Cerebral aneurysm perforation	Putamen haemorrhage
Cerebral aneurysm ruptured syphilitic	Ruptured cerebral aneurysm
Cerebral arteriovenous malformation haemorrhagic	Spinal cord haematoma
Cerebral artery perforation	Spinal cord haemorrhage
Cerebral haematoma	Spinal epidural haematoma
Cerebral haemorrhage	Spinal epidural haemorrhage
Cerebral haemorrhage foetal	Spinal subarachnoid haemorrhage
Cerebral haemorrhage neonatal	Spinal subdural haematoma
Cerebral microhaemorrhage	Spinal subdural haemorrhage
Encephalitis haemorrhagic	Subarachnoid haematoma
Epidural haemorrhage	Subarachnoid haemorrhage
Extradural haematoma	Subarachnoid haemorrhage neonatal
Haemorrhage intracranial	Subdural haematoma
Haemorrhagic cerebral infarction	Subdural haematoma evacuation
Haemorrhagic stroke	Subdural haemorrhage
Subdural haematoma evacuation	Subgaleal haematoma
Subdural haemorrhage	Thalamus haemorrhage
Subdural haemorrhage neonatal	Traumatic intracranial haemorrhage
